# LIST OF ABBREVIATIONS

Abbreviation	Definition
ACEND	Assessment of Caregiver Experience with Neuromuscular Disease
AE	Adverse event
ALT	Alanine Aminotransferase (SGPT)
ANCOVA	analysis of covariance
aPTT	Activated Partial Thromboplastin Time
AST	Aspartate Aminotransferase (SGOT)
AUC	Area under the curve
BLQ	Below limit of quantification
BUN	Blood Urea Nitrogen
CGIC	Clinical Global Impression of Change

Study: 232SM203

Statistical Analysis Plan Version: 1.0

CGIC	Clinical Global Impression of Change
CHOP INTEND	Children's Hospital of Philadelphia Infant Test of Neuromuscular Disorders
CO2	Carbon dioxide
COVID-19	Coronavirus disease 2019
CRF	Case report form
CSF	Cerebrospinal fluid
CV	Coefficient of variance
EAC	Endpoint adjudication committee
ECG	Electrocardiogram
GGT	Gamma-Glutamyl Transferase
HFMSE	Hammersmith Functional Motor Scale – Expanded
HINE	Hammersmith Infant Neurological Examination
HRQOL	Health-related quality of life
ICF	Informed consent form
ІСН	International Council for Harmonization
IDMC	Independent data monitoring committee

Study: 232SM203

Statistical Analysis Plan Version: 1.0

INR	International Normalized Ratio
IRT	Interactive response technology
ITT	Intent-to-Treat
JRT	Joint Rank Test
LLOQ	Lower Limit of Quantification
LP	Lumbar puncture
L3M6	3 loading doses maintenance dose every 6 months
MI	Multiple imputation
NfL	Neurofilament Light chain
PASA	Parent Assessment of Swallowing Ability
PD	Pharmacodynamic(s)
PedsQL	Pediatric Quality of Life Inventory ™
PMS	Post-marketing surveillance
PPS	Per protocol Set
РТ	Prothrombin Time
QoL	Quality-of-life
QTcF	Corrected QT interval using Fridericia's formula

Study: 232SM203

Statistical Analysis Plan Version: 1.0

RULM	Revised Upper Limb Module
SAE	Serious adverse event
SD	Standard deviation
SE	Standard error
SMA	Spinal muscular atrophy
SMN	Survival motor neuron
SMN1	Survival motor neuron 1
SMN2	Survival motor neuron 2
SOC	System Organ Class
ULN	Upper Limit of Normal
US	United States
WHO	World A12:B65Health Organization

### 1. Introduction

This Statistical Analysis Plan is based on Version 6 of the protocol, dated 05May2022. All references to the protocol refer to Version 6.

Nusinersen is an antisense oligonucleotide administered intrathecally via lumbar puncture (LP); it increases survival motor neuron (SMN) protein expression and significantly improves motor function in patients with spinal muscular atrophy (SMA). Nusinersen was approved for the treatment of SMA under the tradename Spinraza™ in the United States (US), European Union, and other countries. The population for this study includes participants with infantile-onset and later-onset SMA.

Efficacy and safety results across the nusinersen clinical development program have demonstrated an overall positive benefit-risk profile of nusinersen across a broad range of SMA phenotypes and patient populations. Nusinersen is approved in the US, Europe, and other countries and regions for the treatment of SMA in paediatric and adult patients at a recommended dosage of 12 mg administered in 3 loading doses at 14-day intervals, a fourth loading dose 30 days after the third dose, and maintenance doses every 4 months thereafter in most countries and regions. Pharmacokinetic (PK) and pharmacodynamic (PD) analyses indicate that nusinersen drug exposure higher than that achieved with 12 mg in patients with SMA may produce an even greater benefit in motor function. Additionally, PK modelling and simulations identified dosing regimens that achieve higher drug exposure more rapidly. Therefore, this study is being conducted to investigate the efficacy, safety, tolerability, and dosing regimen targeted to achieve higher drug exposure more rapidly. This study will be conducted in participants with genetically confirmed SMA.

This is a 3-part study Part A, Part B (infantile-onset and later-onset), and Part C.

Part A was an open label safety evaluation in which later-onset SMA subjects received 3 loading doses of 28 mg of nusinersen and 2 maintenance doses of 28 mg. All 6 participants enrolled in Part A completed.

Part B was double-blind, active-controlled controlled study designed to evaluate the proposed higher dosing regimen and included infantile and later-onset SMA participants.

Part C was an open label safety evaluation in which infantile and later-onset SMA of the participants, who were on the currently approved dose of nusinersen (12-mg maintenance for at least 1 year after the initiation of treatment) received higher dosing regimen via the administration of a single bolus dose of 50 mg of nusinersen (which should be administered 4 months  $\pm$  14 days after their most recent maintenance dose of 12 mg), with maintenance dosing at 28 mg thereafter. All 40 participants enrolled in Part C completed.

#### 2. Study Overview

#### Study Objectives and Endpoints applicable to Part B later-onset.

This analysis plan it is only for Part B Later-onset analyses. Separate SAPs will cover the planned analyses for other parts of DEVOTE and the Part B infantile onset population.

Product: Nusinersen
Study: 232SM203

The Part B primary objective is not applicable to the later-onset population.

#### Secondary Objectives

To examine the clinical efficacy of nusinersen administered intrathecally at higher doses compared to the currently approved dose in participants with SMA.

#### Secondary Endpoints

[figure not shown]
- Change from baseline in Hammersmith Functional Motor Scale Expanded (HFMSE) score.
- Change from baseline in Revised Upper Limb Module (RULM) score.
- Total number of new World Health Organization (WHO) motor milestones
- Change from baseline in neurofilament light chain (NfL) concentration in plasma.
- Change from baseline in neurofilament light chain (NfL) concentration in CSF.
- Change from baseline in Assessment of Caregiver Experience with Neuromuscular Disease (ACEND)
- Change from baseline in Pediatric Quality of Life InventoryTM (PedsQL)
- Number and duration of hospitalizations.
- Clinical Global Impression of Change (CGIC) [physician, caregiver] at Day 302
- Number of serious respiratory events
- Ventilator use
- Change in the Parent Assessment of Swallowing Ability (PASA) scale.

#### **Secondary Safety Objectives**

To examine the safety and tolerability of nusinersen administered intrathecally at higher doses to participants with SMA.

Secondary Safety Endpoints

- Incidence of AEs, including SAEs
- Shifts from baseline in clinical laboratory parameters, ECGs, and vital signs
- Change in growth parameters
- Shifts from baseline in coagulation parameters (aPTT, PT, and INR)
- Change in urine total protein
- Change from baseline in neurological examination outcomes
- The proportion of participants with a post baseline platelet count below the lower limit of normal on at least 2 consecutive measurements
- The proportion of participants with a post baseline QTcF of > 500 msec and an increase from baseline to any post baseline timepoint in QTcF of > 60 msec

# 2.1. Study Design

This 3-part study will evaluate the efficacy and safety of a higher dosing regimen of nusinersen in approximately 145 participants. The study will be conducted at approximately 65 sites globally. Following the completion of this study, all eligible participants may elect to enrol in a separate long-term extension study (232SM302), pending study approval by ethics committees and the appropriate regulatory authorities. In regard to participants rolling over from Part B, this will be done without unblinding the participant's treatment group.

Part B will consist of a pivotal, double-blind, active-controlled treatment period with either 2 or 4 loading doses of nusinersen (for the 50/28-mg Group and Control Group, respectively) administered intrathecally followed by maintenance doses approximately every 4 months thereafter. Approximately 75 participants with infantile-onset SMA and 24 participants with later-onset SMA will be randomized in a 1:2 ratio to receive either the currently approved dosing regimen or a 50/28-mg dosing regimen.

In the Control Group, up to a total of 8 participants will receive 4 loading doses of 12 mg of nusinersen administered intrathecally (Days 1, 15, 29, and 64), followed by maintenance doses of 12 mg on Days 183 and 279 (and a sham procedure on Day 135).

In the 50/28-mg Group, up to a total of 16 participants will receive 2 loading doses of 50 mg of nusinersen administered intrathecally (Days 1 and 15) and 2 sham procedures on Days 29 and 64, followed by maintenance doses of 28 mg on Days 135 and 279 (and a sham procedure on Day 183). In order to maintain blinding sham procedures will be used as shown in the table below.

Arm	Dose 1	Dose 2	Dose 3	Dose 4	Dose 5	Dose 6	Dose 7
50/28-mg	D1	D15	D29	D64	D135	D183	D279
Group	(50 mg)	(50 mg)	(sham)	(sham)	(28 mg)	(sham)	(28 mg)
Control (12/12	D1	D15	D29	D64	D135	D183	D279
mg)	(12 mg)	(12 mg)	(12 mg)	(12 mg)	(sham)	(12 mg)	(12 mg)
Group							

Randomization in Part B will be performed using interactive response technology (IRT).

Product: Nusinersen	Statistical Analysis Plan
Study: 232SM203	Version: 1.0

For Part B later-onset participants, the randomization will be stratified by age at informed consent as follows:

< 6 years and

 $\geq$  6 years

Blinded safety data will be reviewed on an ongoing basis by the Sponsor and the Medical Monitor. Unblinded safety data will be reviewed on an ongoing basis by an Independent Data Monitoring Committee (IDMC).

#### 2.2. Sample Size Considerations

The sample size for Later-onset SMA in Part B is not based on statistical considerations.

A total of 24 participants with later-onset SMA will be randomized to the Control Group and 50/28-mg Group in Part B in a ratio of 1:2; this will allow the exploration of the safety, tolerability, **and efficacy** of the 50/28-mg dose of nusinersen in this population. If any participants with later-onset SMA enrolled in Part B do not complete the Day 183 dose and assessments (e.g., due to withdrawal) as a result of a public health or humanitarian emergency, up to 4 additional participants may be enrolled at the Sponsor's discretion.

## 2.3. General Trial Conduct Mitigation Strategy under COVID-19 Pandemic or humanitarian emergencies

In order to mitigate risk of missing dosing or assessments during the time of the COVID-19 pandemic, the following has been put into place:

- If a site is not closed due to COVID-19 or humanitarian emergencies and the site enables the participant to attend the visit in-clinic, then delayed visits within a reasonable timeframe are allowed.
- Site transfers are encouraged where possible, so that participants can be transferred to another site for assessment. Instructions are in place to enable sites to do this including transfer of the database and source documents for the patient from the transferring site to the receiving site. This will allow the participant to receive dosing and protocol defined assessments to be made. Dosing can only be performed in the clinic setting due to intrathecal administration. In particular, if screening cannot be performed in the clinic, participants will be screened at a screening site and subsequently transferred to another site to performed in the clinic setting due to intrathecal administration and all assessments for the participant, since dosing can only be performed in the clinic setting due to intrathecal administration.
- A phone visit can be used to collect safety data (AEs, concomitant therapies/procedures)
- Transferring sites are encouraged to enter and clean all data before transferring the participant to the receiving site. The database for a participant will remain with the transferring site until data are entered and cleaned as much as possible, but the transferring site must have access to the participant in IRT and copies of all source documents. Blinding of staff will be maintained as appropriate. Any queries raised later on for data belonging to visits at the transferring site will be cleaned by the receiving site through the source documents, and interaction between monitors at the receiving and transferring sites. The transferring site will no longer have access to the

database for a participant they have transferred but the monitors will. The Subject ID will remain the same when a participant is transferred to another site, but the transfer site can be tracked via the Site ID.

#### 2.4. External Data

Three external datasets will be utilized to provide additional comparisons to the higher dose arm. These will include the CS4 study, CS11 (CS4 extension study) and the Japan PMS study.

### 2.4.1.CS4 Study

CS4 was a phase 3, randomized, double-blind, sham-procedure controlled study to assess the clinical efficacy and safety of nusinersen administered intrathecally in patients with later-onset spinal muscular atrophy. The study had a planned follow-up from first dose of 15 months.

Key eligibility criteria were onset of symptoms of SMA at > 6 months of age, aged between 2 and 12 years and ability to sit but never have achieved the ability to walk independently. The primary endpoint was the change in HFMSE score from baseline to Month 15 and secondary endpoints included the proportion of participants achieving a 3 point improvement on the HFMSE, change in RULM and proportion of participants achieving new WHO motor milestones.

The first patient was dosed in November 2014 and the last patient visit was February 2017. The study was stopped early based on the results of an interim safety and efficacy analysis and the study results were published (Mercuri et al. 2018).

A difference between CS4 and later-onset part B of 232SM203 was that in CS4, patients received 3 loading doses of 12 mg at days 1, 29, and 85 and then a dose at Day 274 in contrast to 232SM203 where 4 loading doses at Days 1, 15, 29 and 64 and then a dose at Day 183 is administered consistent with the nusinersen label in the majority of geographies.

# 2.4.2.CS11 Study

This was an open-label extension study in participants with SMA who previously participated in investigational studies of nusinersen. The last participant completed the study on 21Aug2023. The primary purpose of this study was to gather additional information on the long-term safety, tolerability, and efficacy of repeated doses of nusinersen. Participants who were randomized to receive sham control in CS4 switched to receive 12 mg nusinersen at the start of CS11, so this dataset provides additional patients who were naïve to treatment.

# 2.4.3. Japan PMS Study

This is an ongoing, observational study to survey all the SMA patients treated with nusinersen after the launch in Japan for the purpose of understanding the safety and effectiveness in Japanese patients. Patients are followed up to death, discontinuation of the treatment or the end of the study period (8 years after the launch), whichever occurs first. The dosing regimen approved in Japan for later onset participants is the 3 loading doses and 6 monthly maintenance dosing. As part of the effectiveness assessment, HFMSE has been collected at Day 274 dosing for later-onset patients. The latest data cut was at 30th of May 2023.

#### 2.4.4. Summary of external data

The study design for 232SM203 included inclusion/exclusion criteria and efficacy assessments which are consistent with CS4, CS11 and the PMS study. Although the same dose of 12 mg is administered a number of differences exist and these are summarized in the following table.

#### Summary table of external data

	232SM203	232SM203 Standard dose	CS4	CS4 Sham	CS11	PMS
	Higher Dose	Standard dose	nusinersen	Snam		
Loading regimen	2 x 50mg doses	4 x 12mg doses	3 x 12mg doses		3 x 12mg doses	3 x 12mg doses
Maintenance regimen	28mg every 4 months	12 mg every 4 months	12mg every 6 months		12mg every 6 months	12mg every 6 months
Label for regimen		12mg L4M4	12mg L3M6		12mg L3M6	12mg L3M6
Timepoints efficacy collected (a)						
Month 6	Day 183	Day 183 [4]	Day 169 [3]	Day 169	NA	NA
Month 9	Day 279	Day 279 [5]	Day 274 [3]	Day 274	Day 265 [3]	Day 274 [3]
HFMSE collected	Yes	Yes	Yes	Yes	Yes	Yes
RULM collected	Yes	Yes	Yes	Yes	Yes	No
WHO motor milestones collected	Yes	Yes	Yes	Yes	Yes	No(b)
Estimated number of subjects	16	8	84	42	38(c)	27 (d)

a) Number in square brackets denotes the number of 12mg doses received prior to timepoint. So although in 232SM203 a dose is administered at Day 183 this is not counted in the 4 doses shown at Month 6.

[figure not shown]
b) WHO as collected in the PMS study uses different questions and is not considered comparable.

c) Subjects with baseline age 2 to <=10 years with HFMSE >=10 and <=54 and able to sit and never walked alone per WHO motor milestones.

d) Estimated based on data received Jan 2024. SMA type 2 patients, baseline age 2 to <=10 years with HFMSE >=10 and <=54.

# 2.4.5. Summary of How External Data Will be Used in the Analysis

In addition to the main comparison between the two active arms in study 232SM203, external data will be utilized for the following supportive analyses:

# 3. Definitions

### 3.1. Dates and Points of Reference

- Study Day 1: the date of the first dose of study treatment in 232SM203
- Study Day
  - $\circ \quad \mbox{For a date on or after Study Day 1}$

Study Day = (Date of Interest) - (Study Day 1) + 1

• For a date before Study Day 1

Study Day = (Date of Interest) – (Study Day 1)

In order to distinguish nominal visit names from duration defined in days, visit names will be referred to as "Day 15", "Day 29", etc., and "15 days" or "29 days", etc. will be used to define time intervals.

Overall time on study will be defined as the total number of days a participant is known to be followed on study calculated as follows:

Overall time on Study = (Last date on study) – (Date of first dose) +1

Last date on study is defined as the date of the latest visit or evaluation or telephone contact, or time of death from all available data for a given participant.

Disease duration is defined as time from age at symptom onset to age at informed consent.

#### 3.2. Study Treatments

The main presentations of data will be as follows:

Baseline characteristics, disposition, exposure, time on study and adverse event displays

	232SM203	
12/12 mg nusinersen	50/28 mg nusinersen	Total

For baseline summaries including external data, all patients available in the pool will be included in the first column and then the matched patients, in the  $2^{nd}$  column.

|--|

Product: Nusinersen			Statistical Analysis Plan
Study: 232SM203			Version: 1.0
Shar	n	Sham	50/28 mg nusinersen
For efficacy endpoints, s	afety other than AES,		:
For efficacy endpoints, s	afety other than AES,		:
For efficacy endpoints, s		SM203	

For summaries of adverse events and efficacy including external data:

Matched CS4	232SM203
sham	50/28 mg nusinersen

The total study duration for each participant will be approximately 323 to 420 days:

- Screening: 21 days
- Loading period: 64 days
- Maintenance period: 215 days
- Follow-up: 23 to 120 days

# 3.3. Key Derived Variables

Not applicable.

# 3.4. Stratification Factors and Subgroup Variables

Randomization was stratified as follows:

- Age at informed consent:
  - < 6 years and

  - $\geq 6$  years.

The subgroup categories are the following:

 One group comprising North America, Taiwan and Europe (excluding Russia) (regions contributing participants to original 12mg studies) versus another group comprising all other countries.

#### 3.5. Analysis Sets

[figure not shown]
#### 3.5.1. Within 232SM203

The Safety Set

The Safety Set is defined as all participants who receive at least one dose of nusinersen; participants will be analyzed in the treatment group based on what treatment they actually received.

#### The Intent-to-Treat (ITT) Set

The Intent-to-Treat (ITT) Set is defined as all participants who are randomized and receive at least one dose of nusinersen; participants will be analyzed in the treatment group to which they are randomized. This will be the primary population for the analysis of efficacy endpoints.

#### **Per Protocol Set**

A Per Protocol Set will include the subset of the ITT Set who have no significant protocol deviations that would be expected to affect efficacy assessments.

Significant protocol deviations will be determined prior to database lock and will include:

- Participants who had onset of signs and symptoms consistent with SMA at less than or equal to 6 months of age,
- who were younger than 2 years or older than 10 years,
- who cannot sit independently at screening,
- whose HFMSE is <10 or >54 at screening,
- who had respiratory insufficiency at Screening (defined as medical necessity for invasive or non-invasive ventilation for >6 hours during a 24-hour period) gtube at screening or severe scoliosis (Cobb angle > 40).
- Participants who took experimental or approved agents for the treatment of SMA, including gene therapy, biological agent, or device, during the study. This includes marketed agents at experimental doses that are being tested for the treatment of SMA (oral albuterol/salbutamol, riluzole, carnitine, sodium phenylbutyrate, valproate, hydroxyurea, etc.).

If participants have missed planned doses/sham but still completed study.

#### 3.5.2. External data

The ITT Set as defined in the final analysis of CS4 will be used for the sham and nusinersen 12mg groups.

For CS11, the CS4 patients sham participants who received from the start of CS11 will be reassessed to determine if they would have qualified for 232SM203 based on fulfilling all the following conditions:

- Aged 2 to <=10 years at first dose
- Baseline HFMSE score  $\geq 10$  and  $\leq 54$

Product: Nusinersen	Statistical Analysis Plan
Study: 232SM203	Version: 1.0

• Able to achieve WHO motor milestone of sitting without support and never achieved WHO walking alone.

Only patients who satisfy these criteria will be considered from CS11 in the matching pool.

For the PMS study a participant will need to meet all the following conditions to be included in the pool of participants:

- SMA type 2.
- Age at onset of symptoms > 0.5 years or missing.
- Aged 2 to <= 10 years at first dose.
- Baseline HFMSE score  $\geq 10$  and  $\leq 54$ .

The following labels will be used to reference external data.

Label	Description
PS matched: CS4 Sham	Formed from the CS4 ITT set of sham control treated patients using a PS matching to select at least 16 comparable to the higher dose group
PS matched: nusinersen - CS4+CS11	Formed from the CS4 and CS11 ITT set of nusinersen treated patients using a PS matching to select at least 16 comparable to higher dose group
PS matched: nusinersen - CS4 only	Formed from the CS4 ITT set of nusinersen treated patients using a PS matching to select at least 16 comparable to higher dose group
PS matched with caliper: nusinersen A (Clinical trials and PMS)	12mg nusinersen participants from CS4, CS11 and Japan PMS study selected to match 232SM203 higher dose using
PS matched with caliper: nusinersen B (Clinical trials)	12mg nusinersen participants from CS4 and CS11 studies selected to match 232SM203 higher dose using
PS matched with caliper: CS4 Sham	CS4 sham participants selected to match 232SM203 higher dose using

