#### Table 2: Visit windows for safety Endpoints in 232SM203

Product: Nusinersen		Statistical Analysis Plan	
Study: 232SM203			Version: 1.0
Day 135	100	159	135
Day 183	160	232	183
Day 279	233	290	279
Day 302	291	348	302

For efficacy endpoints, the actual day of the unscheduled or end of study visits will be considered.

For post baseline visits up to and including Day 64 a +/-7 day window will be used and for visits between Day 135 and Day 302 a +/-14 day window will be used.

The following rules will be implemented for windowing:

- If more than one observation is within the same window, data from the regular scheduled visit will be used for that visit.
- If neither of the observations are from a regular scheduled visit the observation closest to the planned target date will be used. However, if both the observations are equidistant from the target date, the latest one will be used; if repeated measurements are on the same day, then the last measurement will be used.
- If windowing safety data safety data and there is more than one observation in a window for a dosing visit the observation on the day of dosing will be chosen over the observation where dosing did not occur on the same day.
- In windowing laboratory data, if a central and local result is available within the window then the central laboratory result will be chosen.

Study	Windowing
CS4	All dosed subjects will be included, and the Month 6 and Month 9 values collected will be utilized.
CS11	All dosed subjects meeting the re-evaluated conditions will be included. The protocol defined Day 265 visit will be used. If this was not collected since the subject moved to MMDR dosing, then Day 265 will be missing.
PMS study	The HFMSE visit data will be windowed to give Month 9 as study day 274 +/- 15 days. Therefore, study days between 259 and 289 will be considered, if >1 lie in the window the one closest to Day 274 will be selected. If two are equally close, the latest one will be selected.

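### Later-onset SAP: the CS4 pool enters matching without the age limit of 10 years applied to CS11 and PMS controls, so CS4 children older than 10 can be matched as controls

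*SAP*

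**What the plan says.** All references are to the Part B later-onset SAP unless another part is named.

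- **CS4 pool (3.5.2):** "The ITT Set as defined in the final analysis of CS4 will be used for the sham and nusinersen 12mg groups". The labels for the matched sets in the same section again start from the CS4 ITT set.
- **CS4 entry criteria (2.4.1):** "Key eligibility criteria were onset of symptoms of SMA at > 6 months of age, aged between 2 and 12 years", together with sitting and never having walked independently.
- **CS11 pool (3.5.2):** former CS4 sham patients are "reassessed to determine if they would have qualified for 232SM203 based on fulfilling all the following conditions". The first condition is "Aged 2 to <=10 years at first dose"; the others are a baseline HFMSE of 10 to 54, sitting without support and never having walked alone. The section then adds: "Only patients who satisfy these criteria will be considered from CS11 in the matching pool".
- **PMS pool (3.5.2):** the same age limit applies, with conditions on SMA type, age at onset and HFMSE.
- **232SM203 itself (3.5.1, Per Protocol Set):** significant deviations include participants "who were younger than 2 years or older than 10 years".
- **Windowing table for external data (4.4):** for CS4, "All dosed subjects will be included, and the Month 6 and Month 9 values collected will be utilized". For CS11 the corresponding entry is limited to dosed subjects who meet the re-evaluated conditions.
- **Summary table of external data (2.4.4):** estimated pools are 84 (CS4 nusinersen), 42 (CS4 sham), 38 (CS11) and 27 (PMS). The CS11 and PMS counts carry a footnote with the age limit; the CS4 counts carry none.

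**The concern.** The CS11 conditions have a stated purpose: to keep only patients who could have entered 232SM203. That purpose applies equally to CS4, which is the only sham source and the largest 12 mg source. Yet the age condition is not applied there, and the SAP gives no reason. Section 2.4.4 calls the entry criteria consistent across the studies; on the upper age limit they are not.

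The result is uneven within the plan. In the sets that pool CS4 with CS11, or with CS11 and PMS, one group of controls has passed the age limit and another has not. The CS11 patients are themselves former CS4 sham patients. A child over 10 at both baselines is barred as a 12 mg control from CS11 but remains available as a sham control from CS4.

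Age is the randomisation stratification factor in later-onset Part B and a covariate in its main model. At stake are the external comparisons in section 5.2 (HFMSE, RULM, new WHO milestones, plasma NfL). A control older than anyone eligible for the higher-dose arm has no age counterpart in that arm, and the linear age term then has to extrapolate.

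**Working it through.** The plan states no figure for this point, so the check compares the entry rules and then asks how many children could be involved and whether a filter is feasible.

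**1. Entry rules side by side**

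| Source | Upper age | HFMSE 10 to 54 | Sits, never walked |
|---|---|---|---|
| 232SM203 (Per Protocol Set, 3.5.1) | 10 | yes | sitting listed |
| CS11 pool (3.5.2) | 10 | yes | yes |
| PMS pool (3.5.2) | 10 | yes | SMA type 2 |
| CS4 pool (3.5.2, with 2.4.1) | 12 | yes, per Part C SAP | yes |

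The HFMSE entry for CS4 comes from the Part C SAP, section 5.6.4.1, which describes the CS4 baseline range as 10 to 54. The only mismatch for CS4 is therefore age.

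**2. Upper bound for the sham pool**

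Inputs: 42 CS4 sham patients and 38 eligible CS11 patients (2.4.4). The CS11 patients used are former CS4 sham patients (2.4.2, 3.5.2). A child aged 10 or less at the CS11 baseline was no older at the CS4 baseline.

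- Over-age sham patients: at most 42 − 38 = 4, and 4/42 = 9.5%.
- The bound may be generous, because some of those 4 may be missing from the 38 for reasons other than age.

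**3. Possible presence in the matched sham set (5.1.2, matching designs)**

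- 1:2 design: 32 of 42 taken (76%). If all 4 are selected, 4/32 = 12.5%. If selection ignores age, 4 × 32/42 = 3.0 children.
- 1:1 design: 16 of 42 taken (38%). If selection ignores age, 4 × 16/42 = 1.5 children.

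**4. CS4 nusinersen pool**

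The SAP gives no number and no bound. For an assumed over-age share of 5% to 20%, 84 × 0.05 = 4.2 to 84 × 0.20 = 16.8 children. This range is illustrative only.

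**5. Feasibility after an age filter**

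- Sham: at least about 38 remain, and 32 are needed for 1:2. The 1:2 design would fail only if more than 1 − 32/42 = 23.8% were over age, well above the 9.5% bound.
- 12 mg from CS4, CS11 and PMS: at an assumed 20%, 67.2 + 38 + 27 = 132.2 remain, and 48 are needed for 1:3.
- 12 mg from CS4 and CS11: at an assumed 20%, 67.2 + 38 = 105.2 remain, against 48.

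**The case against.** The strongest reply is that propensity matching exists to pick comparable controls from a wider pool, so a wider pool is not in itself a biased comparison. Three safeguards support this. Additional sets are matched with a caliper, which can reject dissimilar controls. Every model listed in section 5.2 adjusts for age at first dose. An independent statistician without post-baseline data does the matching and may change the algorithm if it fails. All of this stands as mitigation, but none of it excludes a child over 10.

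The different treatment also has a partial reason. CS11 patients had been through CS4 on sham and could have changed, and PMS is an observational survey that needs a filter. CS4 had entry criteria of its own. That explains the absence of HFMSE and motor conditions for CS4, but not the band from 10 to 12 years.

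Part of the matching text is not visible. No section 5.1.3 appears, section 2.4.5 ends at a colon, and the caliper labels in 3.5.2 break off. An age restriction there cannot be ruled out. Every visible statement about the CS4 pool points the other way.

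A reader might infer that over-age children must end up in the sham set because 32 of 42 are needed. That does not follow: 32 are needed only if the 1:2 step is kept, 1:1 is the listed fallback, and with at most about 4 over-age patients a set of 32 can be filled without them.

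**Conclusion.** The inconsistency is real and limited to age. Children older than 10 from CS4 can be matched as sham or 12 mg controls, although the SAP applies an age limit of 10 to the other two external sources and in its own Per Protocol definition.

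Size: at most about 4 of 42 sham patients, hence at most 4 of 32 matched controls at 1:2, and about 3 if selection ignored age. The figure for the 84 CS4 nusinersen patients is unknown.

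A reader might infer that the external comparisons are biased in a known direction, or that CS4 controls fail the 232SM203 criteria more broadly. The documents support neither: no direction or size of bias can be derived, and the other key conditions are already met by CS4 entry. The randomised comparison of the two 232SM203 arms is untouched, since sections 2.4.5 and 5.2 present the external comparisons as supportive and supplementary.

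The conclusion assumes that the 38 in section 2.4.4, which is itself an estimate, consists of former CS4 sham patients, and that the 232SM203 age limit is the one shown in the Per Protocol definition and the CS11 conditions. Confidence is moderate because of the matching text that is not visible. The change is worth making because it is simple and leaves the planned ratios feasible.

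**What to change.** In section 3.5.2, apply the SAP's existing age condition (2 to 10 years at first dose) to the CS4 sham and CS4 nusinersen patients before matching. For sham patients, state that the first sham procedure counts as the first dose. Define every CS4-based matched set from that restricted pool, with and without caliper. Bring the CS4 row of the windowing table in 4.4 into line, and update the 84 and 42 in the 2.4.4 table with a footnote like those for CS11 and PMS. The HFMSE, sitting and walking conditions need not be repeated for CS4.

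If there is a reason to keep the older CS4 children, state it and add a sensitivity analysis restricted to age 10 or less.

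The cost is a few lines of SAP text and one filter in the matching code, run by the independent statistician on baseline data only. The downside is a slightly smaller CS4 pool.
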